## **HYPOTHESIS**

In our study we hypothesize that sub-dissociative-dose ketamine administered as a single agent via breath actuated nebulizer at the dose of 1.5 mg/kg will provide better analgesia at 15 min post-administration with similar rates of side effects in comparison to 0.75 mg/kg and 1 mg/kg for pediatric ED patients presenting to the ED with acute painful conditions. The primary outcome of this trial is the comparative reduction in participant’s pain scores at 15 minutes post medication administration.

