**Data Collection Procedures:** Each patient will be approached by a study investigator for acquisition of written informed consent and Health Insurance Portability and Accountability Act authorization after being evaluated by the treating emergency physician and determined to meet study eligibility criteria. When English will not be the participant's primary language, a staff interpreter or licensed telephone interpreter would be used. Baseline pain score will be determined with an 11-point numeric rating scale (0 to 10), described to the patient as "no pain" being 0 and "the worst pain imaginable" being 10. A study investigator will record the patient's body weight and baseline vital signs. The on-duty ED pharmacist will prepare a breath-actuated nebulizer with doses of 0.75 mg/kg, 1 mg/kg, and 1.5 mg/kg according to the predetermined randomization list, which will be created in SPSS (version 24; IBM Corp, Armonk, NY) with block randomization of every 10 participants. The medication will be delivered to the treating nurse in a blinded fashion and will be administered via breath-initiated nebulization for duration of treatment of 10 minutes.

Study investigators will record pain scores, vital signs, and adverse effects at 15, 30, and 60 minutes. In addition, study investigators will record a residual amount of medication (ml) in the nebulizer after the treatment.

If patients reported a pain numeric rating scale score of 5 or greater and requested additional pain relief at 15 minutes mark post-ketamine administration, intravenous morphine at 0.1 mg/kg will be administered as a rescue analgesic.

All data will be recorded on data collection sheets, including patients' sex, demographics, medical history, and vital signs and entered into SPSS (version 24.0; IBM Corp) by the research manager. Development of the randomization list, confirmation of written consent acquisition for all participants, and statistical analyses will be conducted by the research manager and statistician, who would work independent of any data collection.

Patients will be closely monitored for any change in vital signs and for adverse effects during the entire study period (up to 2 h) by study investigators. Common adverse effects that are associated with sub-dissociative dose ketamine are feeling of unreality, dizziness, nausea, vomiting, and sedation.

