**Data Analysis:** Data analyses will include frequency distributions, paired t-test to assess a difference in pain scores within each group, and independent-sample t-test to assess differences in pain scores between the 3 groups at the various intervals.

Mixed-model linear regression will be used to compare changes in pain numeric rating scale across time points. This will compensate for participants lost to follow-up and allow all patients' data to be analyzed on an intention-to-treat principle.

For categorical outcomes (eg, complete resolution of pain), a  $X^2$  or Fisher's exact test will be used to compare outcomes at 30 minutes. Percentage differences and 95% confidence intervals between the treatment groups will be calculated for all time points with  $P < .05$  to denote statistical significance. Based on the validation of a verbally administered rating scale of acute pain in the ED and the comparison of verbal and visual pain scales, we will use a primary outcome consisting of a minimal clinically meaningful difference of 1.3 between three groups at the 30-minute pain assessment.

**Expected Outcomes:** The primary outcome will include a comparative reduction in pain scores on numeric rating pain scale (NRS) between recipients of nebulized SDK given at three different doses at 15 minutes after analgesic administration. The secondary outcomes will include a need for rescue analgesia at 15, 30 or 60 minutes and adverse events in each group.

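### Adverse events before and after rescue morphine are not separated, so the dose comparison may understate a ketamine side-effect excess at 1.5 mg/kg if the lower doses need more rescue

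*Combined protocol and SAP*

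**What the plan says.** In the combined protocol and SAP, the Hypothesis section states that "sub-dissociative-dose ketamine administered as a single agent via breath actuated nebulizer at the dose of 1.5 mg/kg will provide better analgesia", and it expects this "with similar rates of side effects in comparison to 0.75 mg/kg and 1 mg/kg". It gives no margin for similarity. Study Objectives places side-effect rates alongside analgesic efficacy.

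Under Study Design, Data Collection Procedures sets the schedule: "Study investigators will record pain scores, vital signs, and adverse effects at 15, 30, and 60 minutes". Children are also watched for "adverse effects during the entire study period (up to 2 h) by study investigators". A child who scores 5 or more may receive rescue if he or she "requested additional pain relief at 15 minutes mark post-ketamine administration, intravenous morphine at 0.1 mg/kg will be administered as a rescue analgesic". The common effects of the study drug "are feeling of unreality, dizziness, nausea, vomiting, and sedation".

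Expected Outcomes then says: "The secondary outcomes will include a need for rescue analgesia at 15, 30 or 60 minutes and adverse events in each group". Data Analysis applies a chi-square or Fisher's exact test to categorical outcomes at 30 minutes, and plans percentage differences with 95% confidence intervals between groups at all time points.

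No section asks for the onset time of an adverse event or the time of morphine, splits events by rescue, or says which comparison supports the expectation of similar rates. The rescue rule mentions only the 15-minute mark, whereas the outcome counts need for rescue at 15, 30 or 60 minutes. These two passages must be reconciled, because they determine how many later records can follow morphine.

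**The concern.** The hypothesis is about ketamine given alone. Of the three scheduled adverse-effect records, those at 30 and 60 minutes can follow an opioid, as can the rest of the monitoring period. If dizziness, nausea, vomiting and sedation can also follow morphine, a count by assigned dose mixes the effects of two drugs.

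The mixing need not be balanced. If 1.5 mg/kg relieves pain better, fewer children in that arm should meet the rescue condition, and more morphine goes to the lower-dose arms. Success on efficacy would then move the side-effect contrast towards similarity, which is the other half of the same hypothesis. A dose could be reported as no worse tolerated partly because its comparators received more morphine. The point concerns the safety contrast only, not pain scores after rescue.

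**Working it through.** **Inputs.** The record times, the rescue mark, the list of effects and the 30-minute test come from Study Design. The documents give no sample size, adverse-event rate, rescue rate or morphine event rate, so there is no stated figure to reproduce. Every rate below is an assumption, as is the overlap of morphine effects with four of the five listed effects.

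**Model.** Let *k* be the share of children with a ketamine-caused event, *r* the share given morphine, and *m* the chance that morphine causes an event of the same kind in a rescued child, independently of ketamine. Then

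observed rate = 1 − (1 − *k*)(1 − *r·m*).

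With subscripts L (lower dose) and H (1.5 mg/kg),

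observed excess = (*k*H − *k*L) − *m*·[(1 − *k*L)*r*L − (1 − *k*H)*r*H].

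**Unequal rescue, more at the lower dose.** Take *k* = 0.20 versus 0.35 (true excess 15 points) and *r* = 0.40 versus 0.20. The bracket is 0.80 × 0.40 − 0.65 × 0.20 = 0.19.

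| *m* | Lower dose | 1.5 mg/kg | Observed excess (points) |
|---|---|---|---|
| 0.10 | 23.2% | 36.3% | 13.1 |
| 0.20 | 26.4% | 37.6% | 11.2 |
| 0.30 | 29.6% | 38.9% | 9.3 |
| 0.40 | 32.8% | 40.2% | 7.4 |

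A wider rescue gap (50% versus 20%) with *m* = 0.40 gives 36.0% versus 40.2%, an excess of 4.2 points.

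**Equal rescue.** With *r* = 0.20 in both arms the bracket is 0.16 − 0.13 = 0.03. At *m* = 0.40 the excess is 15 − 1.2 = 13.8 points.

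**More rescue at 1.5 mg/kg.** With *r* = 0.20 versus 0.40 the bracket is 0.16 − 0.26 = −0.10. At *m* = 0.40 the excess is 15 + 4 = 19.0 points, so the bias has reversed. In this example the sign changes once rescue at 1.5 mg/kg exceeds 0.80/0.65 = 1.23 times that at the lower dose.

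**Effect on power, second set of assumptions.** Take *k* = 30% versus 50%, *r* = 40% versus 15%, *m* = 0.30. The observed rates are 0.30 + 0.70 × 0.40 × 0.30 = 38.4% and 0.50 + 0.50 × 0.15 × 0.30 = 52.25%, so a 20-point excess appears as 13.85 points. At an assumed 60 children per arm and two-sided alpha 0.05, power falls from 0.61 to 0.33.

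**What complete masking would need.** With 10% rescue at 1.5 mg/kg, set the two observed rates equal and solve for rescue at the lower dose. For a 10-point excess (30% versus 40%) it must be about 80%, 56% or 37% at *m* = 0.2, 0.3 or 0.5. For a 20-point excess (30% versus 50%) it must be about 64% at *m* = 0.5; at *m* = 0.3 the solution is 102%, which is impossible.

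**The case against.** The strongest reply is that the plan already holds much of the answer. Rescue starts at the 15-minute mark, so the 15-minute record is at or before morphine in every child, and between-group percentage differences are planned at all time points. Need for rescue is also noted at the same times as adverse effects, which permits a coarse split. This stands. What is missing is a statement that the 15-minute comparison has this role, and the times needed to interpret later events.

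Second, counting all events by assigned dose is a legitimate treatment-policy comparison. That also stands, and it should be kept. It does not answer a question about ketamine as a single agent.

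Third, a reader might infer that the plan attributes every event to ketamine. The documents do not say so. They speak only of events by group, and the intention-to-treat sentence belongs to the pain-score model. That all events will be counted by assigned dose, and that the 30-minute test will be applied to adverse events, are inferences from the lack of any other rule.

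Fourth, feeling of unreality is not among the effects assumed to overlap with morphine, so a separate comparison of that effect would be little affected.

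**Conclusion.** The point holds as a conditional one. Following the plan as written can mix morphine effects into the dose contrast for side effects. If the lower doses need more rescue, a true excess at 1.5 mg/kg may be understated: in the main example, 13.1 to 7.4 of 15 points remain.

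A reader might go further and infer that the excess would be hidden, or that the bias must favour 1.5 mg/kg. Neither is supported. In every 15-point scenario above with more rescue at the lower dose, an excess of at least 4.2 points is still visible, and complete masking needs a small true excess or a large rescue gap with frequent morphine effects. The direction depends on unequal rescue, which the efficacy hypothesis implies but no data in the documents show.

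The figures rest on assumed event, rescue and morphine rates, on independence of the two drugs' effects, and on a single any-event rate that the plan does not define. They show the mechanism and are not a forecast.

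**What to change.** - Record the onset time of each adverse event and the time of any morphine.
- Name the 15-minute record, which is already collected, as a stated between-dose side-effect comparison in all randomized children.
- Report each listed effect by assigned dose, split into before and after morphine, beside all events to the end of monitoring and the number rescued per arm.
- Claim similar rates for ketamine as a single agent only if the pre-morphine and all-event comparisons agree, using the planned differences and 95% confidence intervals. Write down before unblinding what counts as agreement. Do not rest the claim on the short window alone.

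The cost is one or two time fields and one extra table. Onset times that are not captured at the bedside cannot be reliably recovered later. The real downside is that the pre-morphine set has shorter follow-up in rescued children and can miss late ketamine effects, which could itself favour similarity. That is why both sets are needed. The rescue rule itself is not altered by any of this.
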